13.3 General statistical methods

The total number of individuals for each of the following categories will be presented: screened for eligibility, screen failures, consented individuals, vaccinated individuals with 1, 2 and 3 doses, participants completing the study follow-up period, and reason for follow-up discontinuation. Participant demographics and baseline characteristics will be described and compared between trial arms.

The ATP population will comprise randomized participants in arms A-G who received three doses of their allocated study vaccine in the allocated schedule and have at least one post-third dose vaccination blood sample (for immunogenicity analyses) or at least one carriage sample at 18 months of age (for carriage analyses). This population will be used for the primary endpoint analysis of non-inferiority.

The ITT population will include all randomized participants who received at least 1 dose of their allocated vaccine schedule, who submitted at least one immunological/carriage sample and for whom the eligibility criteria were correctly applied.

The safety population will include all subjects in trial arms A-F who received a study vaccine. Adverse events occurring during the study follow up period will be analysed and compared between groups. This will be a descriptive analysis and will include adverse events which started on or after the day of vaccine administration for each dose up to and including 28 days later.

A detailed statistical analysis plan (SAP) will be finalized after the study has started (and before the database lock).

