13 STATISTICAL ANALYSES

13.1 Primary analyses and Sample size

The primary endpoint of non-inferiority will be reached if the lower CI around the ratio of geometric mean concentration (GMC) of IgG (fractional/full dose) is ≥ 0.5 (i.e. the 2-fold criterion) at 1-month post-boost dose (10 months of age).

A secondary endpoint will assess the proportion of ‘responders’, defined as those with serotype-specific IgG antibody concentration ≥ 0.35 mcg/ml[13] at 4 weeks after the primary series (18 weeks of age). Non-inferiority will be achieved if the lower limit of the 95% confidence interval (CI) around the difference in the proportion of ‘responders’ (fractional dose group – full dose group) is $> -10\%$ [76] post-primary series (18 weeks of age) for at least 8 of the 10 vaccine types in the PCV10 arms and at least 10 of the 13 vaccine types in the PCV13 arms. Assessments of non-inferiority will be made separately for each of the vaccine type serotypes. Our primary endpoint will be reached across all arms if non-inferior immunogenicity is achieved for the 10 serotypes in PCV10 as this is the standard of care in Kenya currently.

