A co-primary analysis, which has a precedent in PCV licensure analyses[83], will determine whether the immune responses elicited by the fractional doses (20% and 40% doses) are non-inferior to the lowest serotype-specific immune response elicited by the full dose PCV, 4-weeks after the primary series. In PCV13 licensure analyses, the immunogenicity of new PCV13 serotypes, not included in PCV7, were assessed in non-inferiority comparisons with the lowest response observed among the PCV7 serotypes in PCV7 recipients, the response to serotype 6B, for which there was existing evidence of both efficacy and programmatic effectiveness[83]. In adapting this approach to our study, non-inferiority will be achieved if the lower limit of the 95% confidence interval (CI) around the difference in the proportion of 'responders' (fractional dose serotype 'x' – full dose 6B) is >-10%.

The timing of the primary endpoint, at 4 weeks after the booster dose, aligns with the aim to assess the effectiveness of the whole three dose schedule (rather than partial vaccination with 1 or 2 doses). It will give an indication of protection in the second year of life, this is clinically relevant as it is thought that the enhanced protection in the second year of life, as a result of a booster dose, has an important impact on carriage and transmission in toddlers, which may enhance herd protection, compared to a 3p+0 schedule[20]. In a 2p+1 schedule in Kenya, a smaller proportion of children may reach the protective threshold of antibodies after the 2 primary doses in early infancy, compared to after three primary doses, but in the context of low rates of disease after 6 years of PCV10 implementation, young infants would be protected by the indirect protection afforded by the reduced transmission of pneumococci. The timing of the endpoint corresponds to previous literature analysing 2p+1 schedules and is in line with standard practice to analyse non-inferiority trials in the ATP population.

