The results from the multiplex opsono-phagocytic assay (MOPA) to all vaccine serotypes plus 6C will be used to compare IgG functionality after 3 full doses of PCV10 or PCV13 with that after 3 fractional doses of PCV10 or PCV13 at 1-month post boost. Antibody function will also be compared between products for comparable schedules. The correlation between IgG concentration and functional activity following a third dose of PCV delivered in a 2+1 schedule will be assessed. Exploratory analyses will derive a functional correlate of protection against carriage using the post booster MOPA titre and vaccine type carriage at 18 months of age for serotypes 19A and 6A.

To evaluate the safety of the fractional dose delivery we will describe:

- the proportion of infants in each trial arm experiencing specified local vaccination site reactions (e.g. redness, swelling) within the 30 minutes immediately after vaccination as observed by study personnel;
- the proportion experiencing local/systemic adverse reactions, e.g. injection site abscess, in the 7 days after vaccination, as reported by mother or the legal guardian who accompanied the infant to the vaccination session at a day 8 visit.

We do not expect to have the statistical power to determine a difference in the risks of injection site abscess between arms as the risk of injection site abscess is expected to be low. Pentavalent vaccine delivered in 10-dose vials in Kenya resulted in 128 abscesses per 100,000 injections[84]. If this baseline level of risk applies to the 3 immunisations given to 1200

children in the fractional dose groups we would expect to see no more than 5 abscesses throughout the whole study.

The sera of all participants in the seventh trial arm (Arm G) will be assayed for immunogenicity to 7 serotypes (the PCV7 vaccine types) at 4-weeks post-primary series only. The proportion of responders in Arm G at 4-weeks post-primary series will be compared to that of the PCV10/13 2p+1 arms at 4-weeks post-primary series. Non-inferiority will be achieved if the lower limit of the 95% confidence interval (CI) around the difference in the proportion of 'responders' (2p+1 - 3p+0) is $>-10\%$ [76]. Assuming the proportion of children reaching the threshold antibody concentration across serotypes at 18 weeks of age is on average 87%[33], with 300 per arm, we would have 85% power to declare non-inferiority using a margin of 10%, accounting for 7 serotype-specific comparisons.

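### Does leaving the analysis set for the 18-week analyses unnamed put those comparisons at risk?

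*Combined protocol and SAP*

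**What the plan says.** Section 13.3 defines one ATP population for arms A-G: randomised infants "who received three doses of their allocated study vaccine in the allocated schedule and have at least one post-third dose vaccination blood sample", with a parallel clause for 18-month carriage samples. Its use is then stated: "This population will be used for the primary endpoint analysis of non-inferiority". Section 13.1 puts that primary endpoint at one month post-boost. The ITT population (at least one dose, at least one sample, eligibility correctly applied) is defined but assigned to no analysis.

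Three analyses use the 18-week serum, and none has a named set:

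- the responder endpoint in section 13.1, judged "post-primary series (18 weeks of age) for at least 8 of the 10 vaccine types in the PCV10 arms", with a parallel count for PCV13;
- in the same section, "A co-primary analysis, which has a precedent in PCV licensure analyses", which compares fractional doses with the "lowest serotype-specific immune response elicited by the full dose PCV, 4-weeks after the primary series";
- in section 13.2, "The proportion of responders in Arm G at 4-weeks post-primary series will be compared to that of the PCV10/13 2p+1 arms".

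Section 13.3 closes with: "A detailed statistical analysis plan (SAP) will be finalized after the study has started (and before the database lock").

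On timing, Table 2a schedules the booster at D228 ± 2 weeks and the next serum at D256 ± 1 week. Section 9.3.7 labels that serum visit D28PB, that is, 28 days post-boost, without a window.

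**The concern.** In arms A-F the third dose is the booster at D228, so no serum counts as post-third-dose until D256. In arm G the third dose is given at D56 (Table 2b), so the 18-week serum at D84 itself qualifies. Applied at 18 weeks, the single ATP rule would discard a valid D84 result in A-F because of something that happened months later, and would do no such thing in G. That is selection on events after the outcome, on one side of a randomised comparison.

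The reading is not far-fetched. One 18-week analysis is labelled co-primary, section 13.1 appeals to the custom of analysing non-inferiority trials in the ATP population, and it sizes an 18-week endpoint with losses counted after the booster.

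A second worry concerns the primary endpoint. If both Table 2a windows are counted from enrolment, the interval from booster to serum could vary widely, and the ATP rule sets no limit on it.

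**Working it through.** **1. Follow-up demanded of each side, if the ATP set were used at 18 weeks.**

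| | Third dose | First qualifying serum | Wait after the D84 serum |
|---|---|---|---|
| Arms A-F | D228 | D256 | 256 − 84 = 172 days |
| Arm G | D56 | D84 | 0 days |

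A missed D256 serum does not always exclude. The rule asks for at least one post-third-dose sample, and half of A-F are also bled at 18 months (section 9.3.5, Table 2a).

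**2. The plan's power for arm G.** Inputs from section 13.2: 87% responders, margin 10 points, 300 per arm, 7 serotypes, stated power 85%. The check takes equal true rates in both arms, an unpooled normal approximation and independent serotypes, with all 7 required to pass:

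Power = [Φ(0.10 / √(0.87 × 0.13 × (1/n + 1/300)) − z)]⁷

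- n = 300, z = 1.645: SE = 0.02746; Φ(3.642 − 1.645) = 0.977; 0.977⁷ = 0.850, which reproduces the plan.
- n = 300, z = 1.96: Φ(1.682) = 0.954; to the seventh power, 0.718.

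The stated 85% therefore needs a one-sided 5% level.

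**3. The same with A-F reduced.** The only loss figure is 5% at four weeks after the booster (section 13.1). Treating all of it as loss after a valid D84 serum is the most that figure allows: 0.05 × 300 = 15 per arm, or 90 of 1,800, leaving 285.

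- z = 1.645: SE = 0.02782; Φ(3.595 − 1.645) = 0.974; to the seventh power, 0.834.
- z = 1.96: Φ(1.635) = 0.949; to the seventh power, 0.693.

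The cost is 1.6 points of power on the plan's basis and about 2.5 points with a two-sided 95% interval.

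**4. Possible bias.** Of 300 infants, 261 respond (87%).

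- All 15 lost are responders: (261 − 15)/285 = 86.3%, a shift of −0.7 points.
- None of the 15 is: 261/285 = 91.6%, a shift of +4.6 points.

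Both are extremes. Loss unrelated to response would remove about 15 × 0.13 ≈ 2 non-responders and leave the rate unchanged. If those lost responded 5, 10 or 20 points less often than those kept, the shift is 0.05 × gap = +0.25, +0.5 or +1.0 points. The plan gives no information on the gap, so the direction is unknown.

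**5. Fractional versus full dose.** Both sides lie within A-F and meet the same rule, so there is no built-in asymmetry. The co-primary comparison is also within A-F. The 300 per arm already allows for the 5%.

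**6. Booster-to-serum interval.** Counted from D0, the extremes are (256 − 7) − (228 + 14) = 7 days and (256 + 7) − (228 − 14) = 49 days. Counted from the booster with the same ± 7 days, they are 21 and 35 days. Sections 8.2, 10.5, 10.7 and 13.1 all time the endpoint at four weeks or one month after the booster or third dose, which agrees with D28PB. The 7-49 range pairs an early booster with a late serum, or the reverse. Any spread falls on all the blinded arms alike. The plan states over 99% power for the GMC-ratio criterion. It gives no SD; with assumed log10 SDs of 0.3 to 0.8 and 285 per arm, power per serotype stays at or above 99.4%.

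**The case for a change.** The best case for acting is that a SAP promised for later does not fill a gap now. Arm G is unblinded from 10 weeks, so its analysis set should be fixed before results are seen, and the edit would cost only words. A 1-point shift at the margin would raise the one-sided error from 0.025 to about 0.05 (285 against 300). The 5% is an assumption, not a ceiling: at 10% or 15% exclusion, arm G power on the one-sided 5% basis would be 81.5% or 79.4%. Arm G also sits inside the ATP set although its sera are assayed only at 18 weeks, which hints that ATP was meant to apply there.

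Part of this stands. The sets are indeed not written down, and a sensible SAP will name them by time point. The rest is weaker. A 1-point shift at 5% loss needs those lost to respond 20 points less often than those kept, and the affected comparison is secondary. Arm G's place in the ATP definition is explained by the carriage clause, since arm G is swabbed at 18 months. The remark about ATP custom comes in the paragraph defending the post-booster endpoint. Using a sampling window as an ATP exclusion is a trade-off: it would remove sera from the primary analysis to narrow a spread that favours no arm.

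**Conclusion.** No change to the plan follows. This is missing detail of the kind that analysts settle in the SAP, which section 13.3 requires before database lock. The three-dose ATP set is assigned to the post-boost endpoint alone, and the harm appears only if someone extends it to 18 weeks, which the plan does not say. If they did, the cost would be at most 15 of 300 results per A-F arm and 1.6 points of power in one secondary comparison (about 2.5 with a two-sided 95% interval). The primary decision would stand. These sizes rest on 5% loss falling wholly after D84, 87% responders in both arms and independent serotypes.

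The timing part changes no conclusion either, because the endpoint is repeatedly timed from the booster or third dose. A separate wording matter remains. The booster is at 9-12 months in section 9.1, 9 months in section 9.2, and D228 ± 2 weeks in Table 2a, which means 8.4-9.8 months for enrolment at 6-8 weeks. The post-boost serum is at 10-13 months in section 11.1, against 9.6-10.5 months from Table 2a. Those passages must be reconciled; no view is taken on which is right, and the choice of analysis set does not turn on it.

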14 DATA MANAGEMENT

14.1 Hardware and software

The CRFs in this study will be entered into an electronic database, e.g. OpenClinica, that is compliant with Good Clinical Data Management guidelines and 21 CFR Part 11 regulations on clinical data management systems for use in clinical trials. This will be done via secure web interface with data checks used during data entry to ensure data quality. The database will be activated for the study only after successfully passing a formal design and test procedure.

Computers will be used for data entry of paper forms. Management and maintenance of computers will lie with the operational support and data managers at the study site.

14.2 Data security, access and back-up

The database will be kept in a locked server-room. Only the system administrators have direct access to the server and back-ups. Passwords (site investigator, statistician, monitor, administrator etc.) will regulate permission for each user to use the system and database, as he/she requires.

All data entered into the CRFs has identifiers attached to it identifying the user who entered it with the exact time and date. Retrospective alterations of data in the database are recorded in an inbuilt audit function. Time, table, data field and altered value, and the person are recorded.

Back-ups of the whole system including the database will be run internally several times per day. Back-ups will be stored in a secure location.

14.3 Direct access to source data/documents

Source documentation will be held securely by the trial team in KWTRP CGMR-Coast. Access will be granted to monitors responsible for quality assurance, for data entry staff and for purposes of medical care. Access will also be granted for audit by statutory authorities and others. Non-study team members will not be granted access. Qualified staff will supervise data collection and entry on a regular basis. Data managers will support onsite data entry teams.

15 QUALITY CONTROL AND QUALITY ASSURANCE

15.1 Choice of investigators

Investigator CVs are detailed in Appendix 3.

15.2 Monitoring

The study will be conducted in accordance with the current approved protocol, ICH GCP, relevant regulations and standard operating procedures.

Internal monitoring by the KWTRP CGMR-Coast monitoring team will be performed according to ICH GCP including but not limited to visits to the clinical sites for study initiation, during the study and a closeout visit. Data will be evaluated for compliance with the protocol and accuracy in relation to source documents. Following written standard operating procedures, the monitors will verify that the clinical study is conducted and data are generated, documented and reported in compliance with the protocol, GCP and the applicable regulatory requirements.

Monitors will participate as detailed in a monitoring plan that will be prepared prior to the study. This will cover instructions for monitoring the main aspects of the implementation of the clinical studies, as follows:

- Study authorizations and approvals and communication with the ethics committees
- Duties and Responsibilities of the Investigator/Institution
- Suitable resources
- Medical care for the participants
- Clinical Study compliance with the agreed protocol
- Laboratory aspects
- Informed consent of participants
- Data management, records and reports
- Sponsor 's Responsibilities
- Responsibilities of the Monitors
- Records of GCP training

15.3 Training to ensure quality of the study

GCP training and protocol-specific training will be delivered to the whole study team. The objective will be to ensure that the study team members are well prepared and trained, and understand the details of the study, the design and the study procedures. A training plan will be maintained, GCP and GDP will be topics of annual refresher training for all staff.

16 INTELLECTUAL PROPERTY

The vaccine products assessed in the clinical trial are all licensed and in routine use, and therefore no product-related IP will arise from this trial. In the unexpected event that other findings lead to IP then KEMRI guidelines will be followed in terms of registering and exploiting the IP.

However, any intellectual property rights that arise from the work will be safeguarded according to the current KEMRI guidelines and the Industrial Property Act of 2001, sections 32, 58 and 80. The scientific and intellectual contributions of all persons involved in the research will be appropriately acknowledged in all publications and presentations arising from the work.

17 TIME FRAME/DURATION OF THE TRIAL

Total study duration is 42 months; timelines will be determined by the receipt of approval from KEMRI ethics committee and the Kenyan Pharmacy and Poisons Board but are estimated as follows, by activity:	Time period following ethical approval
Study staff recruitment, procurement etc.	Month 1 - 6
Community engagement and mobilization	Month 3 - 6
Screening, and vaccinations for main study.	Month 6 - Month 25
Follow Up for main study (overlaps with vaccinations)	Month 6 - Month 34
Feedback to study participants, complete laboratory analyses, complete data analysis and write up	Month 34 – month 42

18 ETHICS

18.1 Human Subjects

Ethical approval will be sought from KEMRI Scientific & Ethics Review Unit (SERU) and the LSHTM Ethics Committee. Written informed consent will be obtained from at least one parent of all infants enrolled onto the study.

The potential risks to participants include risks related to administration of the vaccine:

- The vaccines are licensed products. In children under 5 years, the most frequently reported adverse reactions to PCVs are those associated with all vaccines, these can include one or multiple of the following symptoms: injection site reaction, fever, irritability, drowsiness, restless sleep, decreased appetite, vomiting, diarrhoea and rash.
- Extending the use of the 4-dose multi-dose vial to provide 10 or 20 administrations may increase the risk of injection site reactions e.g. swelling and localised inflammation due to contamination. If 4-dose vials are used, this will be closely monitored.
- Serious reactions to PCV injection are rare and include hypersensitivity reaction generally associated with diphtheria toxin.

Other potential risks are that despite the small dose-ranging study of a pentavalent PCV showing good responses to saccharide doses as small as 0.5 mcg/ml, there is a small risk that

the 20% and the 40% doses may elicit inferior immunogenicity to the full dose in the fractional dose study arms [57]. The unprotected/partially protected children would then not benefit from direct protection of the vaccine but would benefit from the indirect protection generated by the continued routine administration of PCV10 in the national EPI programme, which has led to dramatic decreases in vaccine type carriage[85] and IPD[86]. In the Kilifi Health and Demographic Surveillance System (KHDSS) in 2016, there were 3.2 cases of vaccine-type IPD per 100,000 person years (pyo) in under 5s[87]. This amounts to 1 case every 31,250 person years. Among the 2100 trial participants followed for 1.5 years, we will observe a total of 3,150 pyo – which means there is a 10% chance that we will see one case of vaccine-type IPD in the study, and a 90% change we will see no vaccine-type IPD. one of the advantages of undertaking this study at KWTRP CGMR-Coast is that it has a strong history of IPD surveillance and we will therefore be able to detect IPD if it occurs in the trial population. Any cases observed will be reported to the DSMB. Although the risk of IPD is very small we will establish procedures to detect it at an early stage when treatment can avert a severe outcome; this will be done by providing participants with easy access to study medical staff. Children with signs of sepsis, pneumonia or meningitis will be investigated with bacterial culture of blood and/or cerebrospinal fluids as appropriate to detect the serotype of pneumococcus causing IPD. If any case of IPD occurs, it will be referred to the DSMB as an SAE. Members of staff at the hospitals in Kilifi and Malindi will be engaged by the study team to enable treatment of referrals if necessary and to notify the study team if a participant presents to the hospital in an unscheduled visit. Any child who develops vaccine type invasive pneumococcal disease will be unblinded and withdrawn from the study. If the child was allocated to a reduced dose arm, they will be given full dose PCV10 in three doses 4 weeks apart (if aged <12 months) or 1 dose (if aged ≥12 months).

If, after final analyses, the fractional doses are found to be inferior, all children in those groups will be given a single, full dose booster PCV.

The potential benefits of participation are as follows:

- Participants will be given the phone numbers of study clinicians and local fieldworkers and/or will be able to present at the clinic with any illness and receive free treatment and referral throughout the course of the study. This is in contrast to government-funded care at local clinics, where waiting times may be lengthy and care is not always free of charge. Rapid referral will be made to Hospital in Kilifi or Malindi in case of any serious illness.
- There will be periodic follow up by phone or by home visits in between the study visits near the end of follow up in order to maintain contact with the participant and actively follow up on their health. For trial participants the benefit of increased access to medical care is likely to outweigh the extremely low risk of IPD caused by vaccine type infection.
- If the vaccine is efficacious at low dose, participants in the PCV13 arms will have the added benefit of immunization against three additional serotypes (3, 6A, 19A) contained in the

study vaccine (PCV13) but not contained in the 10-valent vaccine used in the national programme.

